3.2.2 Pembrolizumab

Pembrolizumab will be administered as a 30 minute IV infusion every three weeks at a fixed dose of 200 mg/infusion. Subjects may be dosed no less than 12 days from the previous dose of drug. There are no pre-medications recommended for pembrolizumab on the first cycle.

Treatment of Pembrolizumab Related Infusion Reactions:

Since pembrolizumab contains only human immunoglobulin protein sequences, it is unlikely to be immunogenic, and induce infusion or hypersensitivity reactions. However, if such a reaction were to occur, it might manifest with fever, chills, rigors, headache, rash, pruritus, arthralgias, hypo- or hypertension, bronchospasm, or other symptoms. All Grade 3 or 4 infusion reactions should be reported within 24 hours to the study sponsor as an SAE if it meets the criteria. Infusion reactions should be graded according to NCI CTCAE (Version 5.0) guidelines.

Treatment recommendations are provided below and may be modified based on local treatment standards and guidelines, as appropriate:

NCI-CTCAE Grade	Treatment Modification for Pembrolizumab
Grade 1 – mild Mild transient reaction; infusion interruption not indicated; intervention not indicated.	Decrease the pembrolizumab infusion rate by 50%; remain at bedside and monitor closely for any worsening. The total infusion time for pembrolizumab should not exceed 120 minutes.
Grade 2 – moderate Therapy or infusion interruption indicated but responds promptly to symptomatic treatment (e.g., antihistamines, NSAIDs, narcotics, IV fluids); prophylactic medications indicated for \leq 24 hours.	Stop pembrolizumab infusion. Resume infusion at 50% of previous rate once infusion-related reaction has resolved or decreased to at least Grade 1 in severity, and monitor closely for any worsening.
Grade 3 or Grade 4 – severe or life-threatening Grade 3: Prolonged (e.g., not rapidly responsive to symptomatic medication and/or brief interruption of infusion); recurrence of symptoms following initial improvement; hospitalization indicated for clinical sequelae. Grade 4: Life-threatening consequences; urgent intervention indicated.	Stop pembrolizumab infusion immediately and disconnect infusion tubing from the subject. Subjects have to be withdrawn immediately from pembrolizumab treatment and must not receive any further pembrolizumab treatment.

Table 8: Treatment Modification for Pembrolizumab

CTCAE Grade	Treatment Modification for Pembrolizumab
-------------	--

- Once the pembrolizumab infusion rate has been decreased by 50% or interrupted due to an infusion-related reaction, it must remain decreased for all subsequent infusions.

- If the subject has a second infusion-related reaction Grade ≥ 2 on the slower infusion rate, the infusion should be stopped and the subject should be removed from study treatment.

- If hypersensitivity reaction occurs, the subject must be treated according to the best available medical practice.

IV=intravenous, NCI-CTCAE=National Cancer Institute-Common Terminology Criteria for Adverse Event, NSAIDs=nonsteroidal anti-inflammatory drugs.

3.2.3 Additional Modifications for Subjects with Grade 2 Infusion-Related Reactions

If, in the event of a Grade 2 infusion-related reaction that does not improve or worsens after implementation of the modifications indicated in **Table 8** (including reducing the infusion rate by 50%), the investigator may consider treatment with corticosteroids and the infusion should be stopped for that day. At the next cycle, the investigator may consider the addition of H2-blocker antihistamines (e.g., famotidine), in addition to the mandatory premedication, for select subjects. However, prophylactic steroids are NOT permitted.

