3.1.2 Definition of Dose Limiting Toxicity (DLT)

DLT is defined as:

- Any Grade 3 or greater toxicity that cannot be attributed to a cause other than study treatment during the first two cycles of Course 1 of DAC-THU and/or pembrolizumab therapy such as disease progression or intercurrent illness.
- Any toxicity that cannot be attributed to a cause other than study treatment (DAC-THU and/or Pembrolizumab) that results in study treatment discontinuation.

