3.2.4 Severe Hypersensitivity Reactions and Flu-like Symptoms

A. Symptoms

- Impaired airway
- Decreased oxygen saturation (< 92%)
- Confusion
- Lethargy
- Hypotension
- Pale/clammy skin
- Cyanosis
- B. Management
 - 1. Epinephrine injection and dexamethasone infusion;
 - 2. Patient should be placed on monitor immediately;
 - 3. Alert intensive care unit (ICU) for possible transfer if required.

For prophylaxis of flu-like symptoms, 25 mg indomethacin or comparable NSAID dose (e.g., ibuprofen 600 mg, naproxen sodium 500 mg) may be administered 2 hours before and 8 hours after the start of each dose of pembrolizumab IV infusion. Alternative treatments for fever (e.g., paracetamol) may be given to subjects at the discretion of the investigator.

For Grade 1 Symptoms: (Mild reaction; infusion interruption not indicated; intervention not indicated): Remain at bedside and monitor subject until recovery from symptoms. The following prophylactic pre-medications are recommended for future infusions: diphenhydramine 50 mg (or equivalent) and/or paracetamol 325 to 1000 mg (acetaminophen) at least 30 minutes before additional pembrolizumab administrations.

For Grade 2 Symptoms: (Moderate reaction requires therapy or infusion interruption but responds promptly to symptomatic treatment [e.g., antihistamines, non-steroidal anti-

inflammatory drugs, narcotics, corticosteroids, IV fluids]; prophylactic medications indicated for 24 hours): Stop the pembrolizumab infusion, begin an IV infusion of normal saline, and treat the subject with diphenhydramine 50 mg IV (or equivalent) and/or paracetamol 325 to 1000 mg (acetaminophen); remain at bedside and monitor subject until resolution of symptoms to Grade 1 or less. Resume infusion at 50% rate.

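### Section 3.2.3 contemplates more pembrolizumab after a Grade 2 infusion reaction that fails to respond, where Table 8 makes such a reaction Grade 3 and bars it

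*Combined protocol and SAP*

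**What the plan says.** The number 3.2.3 appears twice in the protocol; this point concerns Additional Modifications for Subjects with Grade 2 Infusion-Related Reactions. Its trigger is a "Grade 2 infusion-related reaction that does not improve or worsens after implementation of the modifications indicated in" Table 8, including the halved infusion rate. In that case "the investigator may consider treatment with corticosteroids and the infusion should be stopped for that day". For selected subjects it then allows an H2-blocker at the next cycle, on top of a premedication that it calls mandatory. Prophylactic steroids are forbidden.

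Table 8 (Section 3.2.2) describes Grade 2 as a reaction that responds promptly to symptomatic treatment. The infusion may restart at half rate once the reaction has resolved or fallen to Grade 1. Grade 3 includes a reaction that does not respond rapidly to medication or a brief interruption, and one whose symptoms return after first improving. For Grade 3 or 4 the subject must be withdrawn from pembrolizumab at once and may never receive it again.

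A footnote to Table 8 adds: "If the subject has a second infusion-related reaction Grade ≥ 2 on the slower infusion rate", then "the infusion should be stopped and the subject should be removed from study treatment".

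Section 3.2.4 describes Grade 2 in similar terms ("Moderate reaction requires therapy or infusion interruption but responds promptly to symptomatic treatment") but, unlike Table 8, names corticosteroids among the treatments: "inflammatory drugs, narcotics, corticosteroids, IV fluids]; prophylactic medications indicated for 24 hours".

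**The concern.** The patient whom 3.2.3 describes has, in most cases, already left Table 8's Grade 2. Section 3.2.3 neither says so nor points to the Grade 3 row. Its heading and trigger keep the Grade 2 label, it limits the stop to one day, and its next-cycle sentence assumes that dosing goes on. Site staff who follow it as written could give pembrolizumab again to someone whom Table 8 permanently excludes. The matter at stake is patient safety.

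**Working it through.** The plan gives no figure for this point, so the main check sets the rules side by side.

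| Course of the reaction | Section 3.2.3 | Table 8 grade row | Table 8 footnote |
|---|---|---|---|
| Never responds to interruption and treatment | Stop for the day; next cycle contemplated | Grade 3; no further pembrolizumab | Does not apply (needs a second reaction at the slower rate) |
| Improves, restarts at 50%, then returns or worsens at Grade 2 or higher | Same | Grade 3 (return after improvement); no further pembrolizumab | Applies: removal from study treatment |
| Responds promptly once corticosteroids are given | Same | Can remain Grade 2, reading Table 8 with 3.2.4 | Does not apply |

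- **Row 1.** Lack of response fails the Grade 2 description and meets the Grade 3 one. Only the Grade 3 row bars re-dosing, and 3.2.3 does not mention it. This is the clearest gap.
- **Row 2.** Table 8 permits a restart only after improvement, so trouble after the restart is a recurrence. Two existing rules prevent re-exposure if either is followed. Section 3.2.3 points to neither.
- **Row 3.** Here 3.2.3 is coherent, and its next-cycle provision should be kept.

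**Size.** Inputs: 7/154 infusion reactions of any grade and 0/154 of Grade 3 to 5 in the pembrolizumab arm of the first-line NSCLC reference trial (adverse-event table, Section 1.2.10); 12 escalation patients and an accrual ceiling of 85 (Section 10).

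- Any grade: 7/154 = 4.5%. Expected: 12 × 0.0455 = 0.55 in escalation and 85 × 0.0455 = 3.9 at the ceiling.
- Grade 3 or higher: the point estimate is 0. The exact one-sided 95% upper bound solves (1 − p)^154 = 0.05, so p = 1 − 0.05^(1/154) = 0.0193, or 1.9%.
- At that bound: 12 × 0.0193 = 0.23 expected in escalation, with probability 1 − (1 − 0.0193)^12 = 0.21 of at least one; 85 × 0.0193 = 1.64 expected at the ceiling.

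These are upper limits for any Grade 3 or higher infusion reaction. The documents do not say what share would be handled under 3.2.3 instead of the Grade 3 row, so no estimate of mishandled cases is given.

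**The case against.** The best defence is that the texts can be read together. Section 3.2.3 is confined to Grade 2. Once a reaction meets the Grade 3 description, Table 8's prohibition governs, and nothing in 3.2.3 lifts it. Re-dosing is implied, not ordered. Section 3.2.2 also lets its treatment recommendations be adapted to local standards.

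Much of this is fair, but it does not remove the conflict. The 3.2.3 trigger itself includes failure to improve, which Table 8 excludes from Grade 2. The Grade 3 instruction is mandatory in tone, and 3.2.3 does not present itself as an exception.

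Other safeguards exist. Section 3.3.6.2 generally requires drug-related events to settle to Grade 1 or baseline before pembrolizumab resumes, Section 3.3.1.1 sets Day 1 recovery criteria, and the infusion rate must stay reduced. They limit the harm but do not replace the bar: a reaction that was slow to settle can satisfy them by the next cycle.

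A reader might infer that 3.2.3 causes dose-limiting toxicities to go uncounted in the 3+3 escalation. The documents do not support that as a direct result. The first DLT criterion in Section 3.1.2, "Any Grade 3 or greater toxicity that cannot be attributed to a cause other than study treatment" in the first two cycles of Course 1, turns on grade. Grade comes from CTCAE v5.0 (Sections 3.2.2, 6.4 and 8.1.4), is assigned by qualified investigators (Section 8.2), and each patient is discussed weekly (Section 7.4.1). A Grade 3 reaction therefore counts whatever is done at the next cycle. The second criterion, "Any toxicity that cannot be attributed to a cause other than study treatment (DAC-THU and/or Pembrolizumab) that results in study treatment discontinuation", would not be met if the patient stayed on treatment, but a correctly graded Grade 3 reaction in that window already meets the first. A missed DLT needs a separate grading error. The Grade 2 label in 3.2.3 might encourage one, but the section does not instruct it.

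**Conclusion.** The conflict is real and worth correcting. For a reaction that never responds, 3.2.3 as written can lead to re-exposure that Table 8 forbids, and no other infusion-reaction rule bars it. For a second reaction of Grade 2 or higher at the slower rate, the footnote already gives the answer and 3.2.3 only lacks the pointer.

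Few patients would be affected. The reference trial saw no infusion reaction of Grade 3 or higher, and the 1.9% upper bound allows 0.23 such events in the escalation phase. This assumes that DAC-THU does not change the infusion-reaction rate and that a first-line NSCLC rate carries over to the other cohorts. A missed DLT is a secondary risk. The Simon designs, sample sizes and response rules are not affected.

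**What to change.** Keep the existing text of 3.2.3, including the optional corticosteroids, the same-day stop and the ban on prophylactic steroids, and make three edits.

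1. After the first sentence, add: *If the reaction is not rapidly responsive to interruption and symptomatic treatment (including corticosteroids), worsens to Grade 3, or recurs after initial improvement, it is Grade 3: follow the Table 8 Grade 3 row (no further pembrolizumab) and assess for DLT under 3.1.2. A second Grade ≥2 reaction on the slower rate is handled under the Table 8 footnote.*
2. Begin the next sentence: *At the next cycle, only for subjects whose reaction responded promptly and remained Grade 2 or lower, the investigator may consider…*
3. Replace the reference to a mandatory premedication with *any premedication given under 3.2.4*. Section 3.2.2 recommends none on the first cycle, and 3.2.4 recommends it for later infusions without requiring it.

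The added text keeps two consequences apart: the Grade 3 row ends pembrolizumab, while the footnote ends study treatment. Table 8 and its footnote stay as they are. The cost is amendment wording only, with no extra patients, visits or tests.

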3.2.4 Severe Hypersensitivity Reactions and Flu-like Symptoms

A. Symptoms

- Impaired airway
- Decreased oxygen saturation (< 92%)
- Confusion
- Lethargy
- Hypotension
- Pale/clammy skin
- Cyanosis
- B. Management
 - 1. Epinephrine injection and dexamethasone infusion;
 - 2. Patient should be placed on monitor immediately;
 - 3. Alert intensive care unit (ICU) for possible transfer if required.

For prophylaxis of flu-like symptoms, 25 mg indomethacin or comparable NSAID dose (e.g., ibuprofen 600 mg, naproxen sodium 500 mg) may be administered 2 hours before and 8 hours after the start of each dose of pembrolizumab IV infusion. Alternative treatments for fever (e.g., paracetamol) may be given to subjects at the discretion of the investigator.

For Grade 1 Symptoms: (Mild reaction; infusion interruption not indicated; intervention not indicated): Remain at bedside and monitor subject until recovery from symptoms. The following prophylactic pre-medications are recommended for future infusions: diphenhydramine 50 mg (or equivalent) and/or paracetamol 325 to 1000 mg (acetaminophen) at least 30 minutes before additional pembrolizumab administrations.

For Grade 2 Symptoms: (Moderate reaction requires therapy or infusion interruption but responds promptly to symptomatic treatment [e.g., antihistamines, non-steroidal anti-

inflammatory drugs, narcotics, corticosteroids, IV fluids]; prophylactic medications indicated for 24 hours): Stop the pembrolizumab infusion, begin an IV infusion of normal saline, and treat the subject with diphenhydramine 50 mg IV (or equivalent) and/or paracetamol 325 to 1000 mg (acetaminophen); remain at bedside and monitor subject until resolution of symptoms to Grade 1 or less. Resume infusion at 50% rate.

3.2.3 CCR Self – Administered Study Drugs Policy

All oral self-administered investigational agents will be properly accounted for, handled, and disposed in accordance with existing federal regulations and principles of Good Clinical Practice. All oral study drugs will be recorded in the patient diary found in **Appendix 2**. This will be used as a memory aide for subjects. The clinical research team will maintain the primary source record.

Subjects should be asked to bring the diary as well as unused study agent and empty containers with them at each study visit. If a subject goes off study while at home, the research nurse will ensure and document the return of the unused oral investigational agents from the participant.

Unused investigational study agents will be disposed and destroyed per CC pharmacy SOPs.

3.3 DOSING DELAYS AND MODIFICATIONS

This study is intended to evaluate the safety and potential efficacy of oral DAC-THU and pembrolizumab as epigenetic immunotherapy in patients with NSCLC, EsC and MPM. The proposed oral DAC dose of ~0.17 mg/kg to be combined with THU ~10 mg/kg administered 60 minutes before oral DAC, is based on non-human primate studies and the Phase 1 clinical trial in SCD which had an identical pharmacologic objective of DAC distribution through tissues with high CDA expression (intestines, liver etc.), and the wide concentration-time profile desired for non-cytotoxic DNMT1-depletion. This dose of DAC administered orally is 10-20% of the FDA-approved dosages administered intravenously and is < 50% of the dose of oral decitabine administered together with another CDA-inhibitor (a THU-analogue) in clinical trials by Astex/Otsuka.

Although it is anticipated that this therapy will be well tolerated at the revised doses, myelosuppression resulting from reprogramming of hematopoietic stem cell differentiation may become dose limiting (50). If dose limiting myelosuppression is observed during the first 2 cycles of Course 1, DAC-THU will be held until toxicities have resolved to Grade 2 or less, and DAC-THU therapy will recommence at the next lower dose, or at the SAME dose if deemed appropriate by the PI, as indicated in the dose escalation schema (**Table 7**). Only one dose reduction will be allowed.

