Grades 1 and 2 events	• Continue DAC-THU therapy at full dose prescribed. Apply maximum supportive care recommendations.	
Grade 3 events	 Apply supportive care. Apply supportive care. If toxicities occur in the first two cycles of therapy and resolve to Grade 1 or less, in 10 days, resume DAC-THU at current dose. If toxicities occur in the first two cycles of therapy and resolve to Grade 1 or less > 10 days following drug hold, resume DAC-THU at next lower dose. If toxicities occur in subsequent cycles and resolve to Grade 1 or less in 21 days following drug hold, resume DAC-THU at SAME dose. If toxicities recur within two cycles of resuming DAC-THU, hold until toxicities resolve to Grade 1 or less, and resume DAC-THU at next lower dose. If toxicities occur in subsequent cycles and resolve to Grade 1 or less, and resume DAC-THU at next lower dose. 	

General Adverse Events	Action		
Grade 4 events	 Grade 1 or less > 21 days following drug hold, resume DAC-THU at next lower dose. If toxicities recur within two cycles after maximal dose reduction, discontinue DAC-THU. Apply maximum supportive care recommendations. Hold DAC-THU therapy until patient meets hematologic criteria for retreatment and resume DAC-THU at next lower dose. 		
	• If recurrence of hematological adverse event after drug hold/ interruptions is observed with treatment at DL-1, in the setting of maximum supportive care measures applied, hold drug once again until patient meets hematologic criteria for retreatment, further dose reduce DAC-THU if possible or discontinue DAC-THU per PI discretion.		

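### Section 3.3 and Table 9 give conflicting DAC-THU restart rules after Grade 3 or greater myelosuppression in the first two cycles, and neither is given precedence

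*Combined protocol and SAP*

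**What the plan says.** Section 3.3 (Dosing Delays and Modifications) deals with dose-limiting myelosuppression in the first two cycles of Course 1. It states that "DAC-THU will be held until toxicities have resolved to Grade 2 or less" and that "DAC-THU therapy will recommence at the next lower dose, or at the SAME dose if deemed appropriate by the PI". It does not separate Grade 3 from Grade 4 and sets no time limit on recovery. It adds: "Only one dose reduction will be allowed".

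Table 9 (Section 3.3.5) has its own hematologic rows:

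- Grade 3, early recovery: "If toxicities occur in the first two cycles of therapy and resolve to Grade 1 or less, in 10 days, resume DAC-THU at current dose".
- Grade 3 in the same cycles, later recovery: "resolve to Grade 1 or less > 10 days following drug hold, resume DAC-THU at next lower dose".
- Grade 3, recurrence within two cycles of resuming: "hold until toxicities resolve to Grade 1 or less, and resume DAC-THU at next lower dose".
- Grade 4, with no cycle limit: "Hold DAC-THU therapy until patient meets hematologic criteria for retreatment and resume DAC-THU at next lower dose". On recurrence at DL-1, after a further hold: "further dose reduce DAC-THU if possible or discontinue DAC-THU per PI discretion".

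Three clauses of Section 3.3.1 bear on how these fit together. Section 3.3.1.1 lists what must hold on Day 1 of each cycle, but its toxicity criterion is non-hematologic only. Section 3.3.1.2 directs that the dose be adjusted by the preceding text and by the tables, joined by a plain conjunction. Section 3.3.1.3 stops DAC-THU if an attributable event has not recovered within 42 days, and counts a tolerable Grade 2 as recovered.

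**The concern.** The protocol itself names myelosuppression as the toxicity that may become dose limiting, so this restart rule is likely to be used. If two parts of the protocol give different answers for the same patient, the restart decision depends on which page the investigator reads. A monitor could then cite the other page as grounds for a deviation.

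Two things are at stake. One is safety at retreatment: whether a patient still at Grade 2 may be dosed again, and whether a patient who has had a Grade 4 event may go back to the full dose. The other is the dose delivered after a hold. Patients treated at the MTD in Phase I are counted in the Phase II cohorts, so this variation carries into the response data as well.

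**Working it through.** **Do the two rules cover the same events?** Section 3.1.2 makes any Grade 3 or greater toxicity in the first two cycles of Course 1 a DLT unless it has another cause. Dose-limiting myelosuppression in Section 3.3 is therefore attributable Grade 3 or 4 hematologic toxicity in those cycles. Table 9's early Grade 3 bullets name the same cycles, and its Grade 4 row applies in any cycle. The overlap is complete.

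**Side by side, first two cycles:**

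| Event | Section 3.3 | Table 9 | Result |
|---|---|---|---|
| Grade 3, recovery threshold | Grade 2 or less | Grade 1 or less | Conflict |
| Grade 3, recovery within 10 days, dose | Next lower, or same if PI chooses | Current dose | Reconcilable through the PI option |
| Grade 3, recovery after more than 10 days, dose | Next lower, or same if PI chooses | Next lower | Conflict if the PI option is used |
| Grade 4, recovery threshold | Grade 2 or less | Retreatment criteria, not defined in 3.3.1.1 | Cannot be compared |
| Grade 4, dose | Next lower, or same if PI chooses | Next lower | Conflict if the PI option is used |

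Table 9's early Grade 3 bullets do not say what to do with a patient at Grade 2. That the hold continues is inferred from their wording and from the recurrence bullet, which says so outright.

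**Does any clause settle it?** Section 3.3.1.2 applies both sources without an order. Section 3.3.1.3 is a stopping limit, and by accepting a tolerable Grade 2 it does not select Grade 1. Preferring the specific rule to the general one does not help, since both are specific to the first two cycles.

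**Size of the dose difference.** The inputs are the per-course DAC doses in Table 7: 2.0 (Level -1), 2.5 (Level 1) and 3.0 mg/kg (Level 2). The relative gap is (same dose − next lower dose) / same dose.

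- Level 1: (2.5 − 2.0) / 2.5 = 20.0%.
- Level 2: (3.0 − 2.5) / 3.0 = 16.7%.

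**One illustration in capsules.** Suppose DAC-THU restarts on schedule at week 7, using the weeks 7 and 8 columns of Section 3.2.1.2, with 5 mg capsules (Section 13.1.5). At 70-79 kg:

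- Level 1 against Level -1: 12 against 10 capsules, 60 against 50 mg, 2/12 = 16.7%.
- Level 2 against Level 1: 15 against 12 capsules, 75 against 60 mg, 3/15 = 20.0%.

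Over all weight bands the gap is 1 to 4 capsules at Level 1 (1/7 = 14.3% to 2/9 = 22.2%) and 2 to 6 capsules at Level 2 (4/23 = 17.4% to 3/13 = 23.1%). This is one scenario only. A cycle 1 event leaves more dosing weeks, and a week 4 event with quick recovery could restart in week 5.

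**The case against.** The best reply is that the two sources are meant to be read together. Section 3.3 gives the general permission (lower dose, or same dose where suitable), and Table 9 says when each applies. On that reading most of the dose conflict disappears and the stricter Grade 1 condition controls. The reading is possible, but the text does not compel it. Where Table 9 intends PI discretion it says so: the thrombocytosis row requires DL-1 in the first two cycles of Course 1 and allows the PI a choice only afterwards. The early Grade 3 bullets and the initial Grade 4 instruction grant none. Section 3.3 therefore adds discretion exactly where Table 9 withholds it.

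Several limits on the point do stand. In the text I have, the Grade 3 row repeats its supportive care step and shows no opening hold instruction, so a bullet may have been lost. That bears on the inferred hold through Grade 2, not on the dose conflict. Section 3.3 is not uniformly looser: its default is the next lower dose, which for Grade 3 recovery within 10 days is stricter than Table 9. Twice-weekly blood counts in Course 1 (Section 3.4.2) and weekly team review (Section 7.4.1) reduce the risk, though they do not say which rule applies.

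A reader might also infer that Table 9 sets a Grade 1 threshold for Grade 4 events. It does not; that threshold is simply undefined.

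**Conclusion.** The protocol is internally inconsistent and wrong as written. For attributable Grade 3 myelosuppression in the first two cycles, the recovery grade needed for restart differs (2 against 1). For Grade 3 recovering after more than 10 days, and for any Grade 4 event, a same-dose option stands against a required reduction. For Grade 4 the conflict is on dose only.

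The planned per-course difference is 20.0% at Level 1 and 16.7% at Level 2, and it arises only if the PI uses the same-dose option where Table 9 requires a reduction. If the option is not used, late Grade 3 recovery leaves only the threshold conflict, and Grade 4 leaves only an undefined threshold.

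A reader might infer that the MTD decision or the Phase II stopping rules are compromised. The documents do not support that. The triggering event is already a DLT before any restart decision is made, and the dose levels and Simon boundaries do not depend on the restart rule. The effect on Phase II is through delivered dose in affected patients, and nothing in the documents allows its effect on response to be estimated.

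These conclusions assume the two-cycle DLT window of Sections 3.1.2 and 3.1.3, and that the Grade 3 row conditions restart on Grade 1 or less as it reads.

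**What to change.** State in Section 3.3 that Table 9 governs hematologic holds. Remove the Grade 2 threshold there, and remove the same-dose option where Table 9 requires a reduction. Add one hematologic retreatment threshold to Section 3.3.1.1 (for example Grade 1 or less, or baseline), refer to it in Table 9's Grade 4 row, and align Section 3.3.1.3 with it. Reconcile "Only one dose reduction will be allowed" with "further dose reduce DAC-THU if possible or discontinue DAC-THU per PI discretion" by stating one cap in both places.

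If the sponsor prefers the flexibility of Section 3.3, it may amend Table 9 instead. That is a clinical choice, but one rule must apply. Two drafting clarifications could go in the same amendment: say what DL-1 means for a Level 2 patient (Level 1 or Level -1), and say what follows a Grade 4 event at Level -1.

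The cost is a wording amendment with its usual review, with no redesign and no added patients. Adopting Table 9 takes some discretion from the PI and may lengthen holds. Whether longer holds would lead to removals is uncertain. Section 3.3.1.3 allows 42 days for DAC-THU toxicity, while Section 3.6.1 lists a three-week delay as a reason for removal; the three-week limit in Section 3.3.2 appears to concern other illness. A patient removed before completing nine weeks of therapy could be non-evaluable for response under Section 6.3.2, so the amendment should also say which delay limit applies.
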